3. STUDY DESIGN

We will use a stepped-wedge randomised controlled trial (RCT) design (Hemming, Haines, Chilton, Girling, & Lilford, 2015). This design involves random and sequential crossover of groups from control to intervention until all groups are exposed to the intervention. A stepped wedge cluster RCT is especially useful when the intervention is thought to do more good than harm (i.e., when there is no equipoise). In that situation, it is unethical to withhold or withdraw the intervention from a proportion of the subjects as would occur in a parallel group or classic cluster RCT. Besides, it may be impossible to implement the intervention in half of all clusters simultaneously because of practical, logistical, or financial reasons, which is also the case in the current study with regard to the practical and logistical reasons. Then, the stepwise treatment implementation of the stepped wedge design offers a solution. Since all patients included in this study will be offered the intervention, which may contribute to limiting lost to follow-up

The personalized approach, local collaborations with the social domain and organizational differences between general practices will result in nuanced differences in how our intervention will be applied. Besides, training the Positive Health methodology and the enhanced collaboration between domains most likely effects patients not-offered the intervention as well. Randomisation will therefore be done by cluster.

This study will be performed in 20 general practices. Each practice will form one cluster. We aim to include an average of 10 patients per cluster. A GP or POH-GGZ can only participate in one cluster. The terms GP practice and cluster will be used alternatively and exchangeable from this point on, both referring to the given description.

Each participating patient starts with a control period and will cross-over to the intervention period. The control period varies between 2 to 8 months. All patients from a GP practice cross-over at the same moment. Therefore the GP-practices are randomized into one of four groups.

All clusters start to collect control data at the same time ($t=0$). The 20 clusters will be divided into four groups evenly and each group will be randomly assigned one of four time points at which they will start to implement the proactive integrated care intervention. The first switch will be after 2 months ($t=2$). Every subsequent 2 months a next group of general practices will switch to the intervention mode until all groups have started the intervention. All groups will continue with the intervention as described in this protocol for a total of 12 months. After the 12 months of intervention, care will be delivered as usual. There is no objection if care providers and patients wish to maintain certain aspects of the intervention. All measurements and timepoints after the switch to the intervention falls under the intervention period. The total duration of this study comprises 22 months. This results in varying control period ranging from 2 to 8 months. The total of intervention and follow-up period vary from 14 to 20 months. This time table is summarized in the following chart.

In order to achieve more accurate answers from patients and in turn more reliable results, a member of the research team will administer the SF-12, and questionnaires on proactive coping (UPCC), and self-efficacy (PAM-13 and SE+IN) during a face to face interview, as these might require extra guidance when filling in. This will be done at three time points for each group (before the start of the intervention, at the end of the intervention, and two months after the intervention has ended).

[figure not shown]

Figure 1. This figure depicts the time schedule of this study. The EQ-5D-5L is administered 7 or 8 times, depending on cluster, and is depicted as a square. The Care and Work questionnaire is depicted with an arrow. The questionnaires PAM, SE+IN, SF-12 and UPCC are administered thrice: at the start and end of intervention and two months after ending the intervention (star). The dot represents the HCCQ and adapted NPS at 6 months after the start of the intervention. Focus groups (triangle) are organised per cluster, after finishing the intervention.

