4.3 Exclusion criteria

For this study exclusion criteria are set for GP practices and for participating patients.

Participants:

- The patient is terminal.
- The patient is living in a residential home.
- The patient has dementia or a disability that prevents them from communicating effectively. The patient already has experience with the positive health tool.
- The patient is not competent to make decisions concerning their health. This will be assessed by the patient's own general practitioner.
- Veto of the GP

Exclusion criteria for GP practices:

- Veto of GP
- The GP or POH-GGZ is already participating in this study in a different cluster.

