4.5 Investigational treatment

The proactive integrated care intervention that will be used consists of five steps:

1. Active invitation of the patient from the practice

2. Consult of 45 minutes with a trained Practice Nurse Mental Health Care based on the Positive Health Methodology. The outcome of this consultation is a spiderweb with an overview of current health status according to positive health methodology.
3. Multidisciplinary Team meeting (MDO) based on the spider web with the domain specific explanation. In this MDO at least the mental health practice nurse, GP, social worker or community nurse are present. The patient is always invited. The outcome of this meeting is: (1) a personalised care plan; (2) appointment of one care coordinator and (3) a structured follow up plan (frequency and duration) of the progression of this patient's problems.
4. Execution of the personalised care plan. The care coordinator has frequent contact with the patient. A minimum of 3 consultations for the first 12 weeks is set, however more frequent consultation can be expected. The proactive nature of this contact is emphasized. A minimum of 4 consultations between patient and care coordinator is set. These minimum amount of consultation is deliberately set to take frequency of consultation as an outcome parameter. The proactive nature will be strongly endorsed, however implementation may differ according to the needs of each individual patient. Given the complex nature of the population the frequency of contact is expected to be higher in the majority.
5. Follow-up of the personalised care plan. During the regular monthly meetings of the health and social care network the follow-up of the patients will be reviewed. Each patient will be discussed at least two times, but more often if necessary. In case the care plan is not followed correctly or it does not have the desired outcome, the patient and the care network will make the needed adjustments to the care plan.

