- As part of process evaluation all involved professionals (GP, POH-GGZ, social workers or other) will be invited to join a focusgroup on their experience with this proactive, integrated care approach and the audio records of the intake and MDO will be scored on the level of shared decision making by two independent observers.
- Collection of data on: medical and acute care utilization, medical costs. (beginning and end of study).

The following time investment will be asked from each patient:

- 10 minutes: invitation of the patient by the GP practice and sharing of information about the study with the patient. Permission to send information about the study, will be asked.
- 10 minutes: follow-up with patient about participation in the study. If the patient agrees to participate, an informed consent form will be send out.
- 170 minutes for the questionnaires: this consists of 4 timepoints of EQ-5D-5L and Care and work questionnaire (4x10min = 40min), two timepoints of psychological questionnaires(SF-12, PAM-13, SE+IN) with EQ-5D-5L and care and work (2x40min = 80min), once EQ-5D-5L with Care and Work and evaluative questionnaire (modified NPS, HCCQ) (1x 10min = 10 min) and once psychological questionnaires combined with EQ-5D-5L (1x40min = 40min).
- 45 minutes: first consultation based on the Positive Health Methodology.
- 60 minutes (2x30=60min): all patients are invited and stimulated to join the multidisciplinary meetings. Patients will be discussed at least at least 2 times during the 12 month period. Additional ad hoc meeting is possible if necessary.
- 10-30 minutes (minimum of 4 times, thus combined total of 40-120 minutes): for the extra meetings that patients are going to have with their care coordinator, according to their personal care plan.
- 60 minutes: focus group focused on the patients their experience with the intervention. Each focus group will be 60 minutes and each patient will only be invited once. This will be done after they end the intervention.

	First three month period	Total 12 months period	Total in study period
POH-GGZ intake	1x45 min	1x 45 min	1x45 minutes
Multidisciplinary meeting	1x30 min	Minimum 2x 30	Minimum 2x 30 minutes
Care coordinator	Minimum of 3x, more frequent contact is	Minimum of 4x in 12 months, however more	Minimum of 4x in 12 months

	possible. Proactive nature of this contact is highlighted.	frequent contact is expected. Proactive nature of contact is highlighted.	
Questionnaires			170 minutes

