7.2 Recruitment and consent

GP practices

The GP-practices affiliated with RadboudUMC, SGZ or affiliated with *Hadoks* will be approached through internal communication. This study is submitted as a single center research in agreement with the METC-LDD on 14-11-2021. The department of Public Health and Primary Care takes responsibility for gathering and storing *onderzoeksverklaring* from each participating GP practice.

Patients

Identification and selection of eligible patients is done as described in chapter 4.1. Patients can be grouped in one of three categories: (1) eligible per GP-list and per algorithm, (2) eligible per GP list and (3) eligible per algorithm. We aim to equally include patients from the GP's selection and the algorithm's. The internal order of these lists are randomised. First, patients who appear on the list of both GP and algorithm are approached for study participation. Then, recruitment alternates between the GP-list and the algorithm list to acquire a 50/50 divide. Invitations stops when there are no more patients to recruit, or when the GP practice reached their maximum number of inclusions.

The GP-practices reaches out to the patient using a script (E3). If patients consent, an information package sent including informed consent forms and a link to an information video. A week later the researchers call to answer questions and to acquire informed consent. In case of consent, patients sign the Patient Informed Consent forms twice and sent both to the researcher. After researcher signs, one copy is stored and one copy is sent back to the patient.

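### The one-cluster rule covers only the GP and POH-GGZ; any social worker or community nurse shared between practices could carry parts of the intervention into control periods

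*Protocol*

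**What the plan says.** The rule that keeps clusters apart appears twice and names the same two roles each time. Section 3: "A GP or POH-GGZ can only participate in one cluster". Section 4.3, as an exclusion criterion for practices: "The GP or POH-GGZ is already participating in this study in a different cluster".

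The team that delivers the intervention is wider. On the meeting that produces the care plan and appoints the care coordinator, section 4.5 says: "In this MDO at least the mental health practice nurse, GP, social worker or community nurse are present". On follow-up, the same section says: "During the regular monthly meetings of the health and social care network the follow-up of the patients will be reviewed". In section 5.3 the professionals invited to the process evaluation are described as "all involved professionals (GP, POH-GGZ, social workers or other".

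As part of its argument for randomising by practice, section 3 states that "training the Positive Health methodology and the enhanced collaboration between domains most likely effects patients not-offered the intervention as well".

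Section 5.2 divides the practices evenly over four start groups with an Excel tool. It mentions no link between practices as a constraint.

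**The concern.** The safeguard stops at the practice's own staff, while part of the intervention is collaboration with people outside the practice. A social worker or community nurse who works with two trial practices in different start groups would take part in the new way of working at the first practice while the second is still delivering usual care. Neither section 3 nor section 4.3 prevents this, and section 5.2 does not stop two such practices from being given different start times.

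Between t=2 and t=8 some groups are in control while others have switched. If part of the intervention reaches control patients in that window, the difference between concurrent groups shrinks. The estimate is then pulled towards no effect and power falls.

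**Working it through.** **1. Who delivers, and who is covered.**

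| Element (section 4.5) | Staff involved | Covered by the one-cluster rule? |
|---|---|---|
| Invitation | the practice | yes, as far as it is done by the GP or POH-GGZ |
| 45-minute intake | trained practice nurse (POH-GGZ) | yes |
| Multidisciplinary meeting | practice nurse, GP, social worker or community nurse | the first two only |
| Care coordination | coordinator appointed in the meeting, profession not restricted | only if GP or POH-GGZ |
| Follow-up | monthly meeting of the health and social care network | only the GP and POH-GGZ in it |

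No other section restricts the uncovered staff to one cluster, asks whether practices share them, or records sharing.

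**2. When it could matter.** By section 3 the groups switch at t=2, 4, 6 and 8. In two-month blocks the number of groups in control is:

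- t=0 to 2: 4
- t=2 to 4: 3
- t=4 to 6: 2
- t=6 to 8: 1

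That makes 4 + 3 + 2 + 1 = 10 control group-periods. The first 4 precede any switch and cannot be contaminated. The other 3 + 2 + 1 = 6 (60%) run while at least one other group has switched.

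**3. Illustration of size.** The protocol gives no rate of sharing or leakage, so there is no figure of its own to reproduce on this point. From section 4.4 I take only the planned 80% power and two-sided 5% alpha, as a nominal starting point. Whether section 4.4 attains 80% is a separate question that this illustration does not settle.

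Let c be the assumed proportion by which the contrast is diluted. The expected contrast is multiplied by (1 − c), and

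power = Φ((1 − c) × (1.960 + 0.8416) − 1.960) = Φ((1 − c) × 2.8016 − 1.960).

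| c (assumed) | Argument of Φ | Power | A true 25% decrease is estimated as |
|---|---|---|---|
| 0% | 0.8416 | 80% | 25% |
| 5% | 0.95 × 2.8016 − 1.960 = 0.7015 | 76% | 23.75% |
| 10% | 0.90 × 2.8016 − 1.960 = 0.5614 | 71% | 22.5% |
| 20% | 0.80 × 2.8016 − 1.960 = 0.2813 | 61% | 20% |

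Here c is the dilution of the whole estimated contrast. If a dilution of 10% or 20% arose only in the 6 exposed blocks, its average over all control time would be 0.6 × 10% = 6% or 0.6 × 20% = 12%. The concurrent comparisons would still carry the full 10% or 20%.

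**The case against.** The case against has real force.

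- **Sharing is not documented.** A reader might infer that it is to be expected, because section 7.2 says "The GP-practices affiliated with RadboudUMC, SGZ or affiliated with *Hadoks* will be approached through internal communication" and section 6 adjusts for neighbourhood. Neither shows it. Section 4.1 provides for practices outside any regional network, and adjusting for neighbourhood does not place two practices in the same one.
- **The practice starts the intervention.** A reader might infer that control care at a linked practice turns into the intervention. Under section 4.5 the invitation, the trained intake and the meeting with the GP still need the practice's own staff. Section 4.2 asks for problems on any two of three domains, so some control patients may have no social problem and no contact with a shared social worker. Only the coordination element is exposed.
- **The spill-over sentence is mainly about individual randomisation.** A reader might take "the enhanced collaboration between domains most likely effects patients not-offered the intervention as well" as an admission of leakage between practices. In context it explains why patients within a practice are not randomised individually, and cluster randomisation answers that.
- **Some information will be collected.** Integration is measured per practice (section 5.1.3) and adjusted for (section 6), and context and fidelity are topics for the professionals' focus groups. This does not identify shared staff. The focus groups are held at t=14 to t=20, after every control period has ended, so they can describe contamination but not prevent it.

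The first three points limit the likelihood and size of the problem. None of the four closes the gap in the rule.

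**Conclusion.** The gap is real but conditional. The one-cluster rule is narrower than the group of people who deliver the intervention, and nothing else in the protocol makes up the difference. Contamination follows only if a social worker, community nurse or care coordinator serves practices in different start groups. It would then be partial, confined to t=2 to t=8, and would normally bias the concurrent contrast towards no effect.

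The documents do not support a stated loss of power. The figures of 76%, 71% and 61% rest on assumed dilutions of 5%, 10% and 20% and on a nominal 80%; if no staff are shared the loss is zero. The point is therefore an inexpensive improvement to the allocation rules, not a demonstrated bias.

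**What to change.** Before randomisation, amend sections 3, 4.3 and 5.2 so that each practice lists its participating social worker, community nurse and likely care coordinators. Practices that share one of them are then allocated to the same start group, as one unit.

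This costs one question per practice and one constraint in the randomisation tool; if no practices are linked, allocation is unchanged. If some are, there are fewer independently allocated units than 20 and the groups may not be five practices each. That cost grows if links chain across many practices, so the number of links should be known before the constraint is fixed.

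If randomisation is already done, record the sharing per practice and per period. Add a sensitivity analysis that keeps the linked control periods and models them as a separate, partly exposed condition. Leaving those periods out should be reported only as a secondary check: it removes concurrent controls, and which periods go depends on the allocation itself.

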4. STUDY POPULATION

4.1 Population (base)

The population consists of individuals that are registered patients at one of the participating GP practices and have at least two incidents of acute care utilisation during the past year. These individuals also have active problems on two of three domains (somatic, mental and/or social problems) based on diagnosis (coded with the International Classification of Primary Care) or medication (ATC) coding. The patients will be identified by analysing data from GP's electronic medical records from the participating GP practises.

An algorithm and the general practitioner both identify eligible patients. This results in two separate, possible overlapping, lists. The general practitioner makes an assessment of possible suitable patients. This list will be checked for in- and exclusion criteria. A combination of the *Adjusted Clinical care Groups*, a risk stratification tool, and a specifically designed algorithm (Girwar, Fiocco, Sutch, Numans, & Bruijnzeels, 2021; Girwar et al., 2022). -- that predicts high acute care utilisation in patients with problems on multiple life domains-- are used to identify eligible patients from routine care data. The 60 highest scoring patients are screened for the inclusion criteria. After that, the GP checks exclusion criteria. In order to run these tools a pseudonymised extraction of HIS-data will be done, including needed data on age, sex, ICPC-, and ATC-codes and number of recent GP-visits. The data-extraction will be performed in two modes depending on whether the GP practice is affiliated within a regional GP network. In practices that are not affiliated, the extraction will be performed in the GP practice using a standalone computer. In practices that are affiliated data extraction will be performed via a trusted third party (ELAN or RadboudUMC).

Patients can be grouped in one of three categories: (1) eligible per GP-list and per algorithm, (2) eligible per GP list and (3) eligible per algorithm. We aim to equally include patients from the GP's selection and the algorithm's. The internal order of these lists are randomised. First, patients who appear on the list of both GP and algorithm are approached for study participation. Then, recruitment alternates between the GP-list and the algorithm list to acquire a 50/50 divide. Inclusion stops when there are no more patients to recruit, or when the GP practice reached their maximum number of inclusions.

4.2 Inclusion criteria

In order to be eligible to participate in this study, the following criteria must be met by the general practice and participating patients.

GP practice:

- There is a POH-GGZ available in the GP practice.
- Planning of a multidisciplinary meeting (MTM or MDO) is a possibility within the GP practice.
- The GP practice is willing to work and share information with different care professionals in the recurring multidisciplinary meetings, to optimise the results of the intervention.
-

Participants:

- The patients are ≥ 18 yrs
- The patients are registered within one of the participating GP practices.
- Patients with at least two acute care encounters in the past 12 months. Acute care encounter is defined as an encounter with out-of-hours GP service, emergency care, acute mental health care or unplanned hospital admittance.
- Patients have problems registered in the GP Information system on at least two out of three of the following domains: somatic, mental or social. Somatic problems is having at least one ICPC code on the problem list. Mental problems is having at least one ICPC code from the "P"-chapter on either the problem list, as a reason for encounter, and/or having medication prescribed related to mental health problems. Social problems is having at least one ICPC code from the "Z"-chapter or as reason for encounter, and/or having medication prescribed related to social problems.

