A stepped-wedge cluster randomised controlled trial (RCT) design will be used. This study will be performed in 20 general practices that do not yet offer proactive integrated care for hotspotters. Data on cost-effectiveness will be quantitatively assessed. Patient experience will be qualitatively assessed through focus groups and quantitative using validated questionnaires. Besides, the process will be both qualitatively and quantitatively evaluated using interviews or focusgroups, observations (audio recording) with care professionals on common themes of process evaluation and a validated questionnaire.

Study population:

In total 200 hotspotters will be included. Hotspotters are individuals with at least two incidents of acute care utilisation (defined as out-of-office GP consultations, acute psychiatric care, emergency department visits and unplanned admissions) during the past year, and problems on two out of three health domains (chronic somatic, mental and/or social problems) based on diagnosis (coded with the International Classification of Primary Care) or medication

(ATC) coding.

Intervention:

The proactive integrated care intervention that will be used consists of five steps:

1. Active invitation of the patient from the practice.
2. Consult of 45 minutes with a trained Practice Nurse Mental Health Care based on the Positive Health Methodology.
3. Multidisciplinary team meeting based on the spider web with domain specific explanation to create a personalised care plan and assign a care coordinator to each patient.
4. Execution of the personalised care plan and frequent pro-active contact between care coordinator and the patient. In the first 12 weeks there is a minimum of 3 contact moments, however more frequent contact is expected. The proactive nature of this contact is emphasized.
5. Follow-up of the personalised care plan using clinical review and at least one multidisciplinary meeting. If needed, ad hoc additional meetings can be organised.

Nature and extent of the burden and risks associated with participation, benefit and group relatedness:

Participation in this study is expected to be low risk for the patients. However, both risks and benefits are associated with participation.

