1. OBJECTIVES

The primary goal of this study is to get insight in the cost-effectiveness after 12 months of working with a proactive, integrated (social) care approach in patients fitting our definition of a hotspotter. A hotspotter is a patient with problems on two out of three health domains (chronic somatic, psychiatric and/or social) and at least 2 acute care activities in the previous 12 months. The medical data from 3 years prior to the start of the study will be used to analyse the costs and utilisation of care. This extended period used for data analysis was deliberately chosen to include a timeframe during and before the SARS-CoV-2 pandemic. Since it is yet unknown how the pandemic and its subsequent measures affected our population and their usage of care.

Hypothesis: We hypothesise that after one year of working with a proactive approach of integrated care to improve the care for patients with problems on two out of three health domains (chronic somatic, psychic and/or social) and at least 2 acute care activities in the previous 12 months will result in reduction in volume and spending of acute care, improvement in experienced health and in patient experience.

Research questions:

Is proactive integrated care cost-effective and result in better patients experience than usual care after 12 months for patients with problems on multiple life domains?

Primary outcomes: Incremental cost-effectiveness from a societal perspective. Information on cost will be based on patient-reported data obtained by questionnaires supplied with data from the GP medical files (*Huisarts informatie system, HIS*) and through CBS microdata. To assess the effectiveness the EQ-5D-5L will be used for determining quality of life.

Secondary outcomes:

Insight into patients experience of care:

Insights into the experiences of care will be gathered during a focus group and information about self-efficacy (PAM-13 and SE+IN itemlist), proactive coping (UPCC), and quality of life (SF-12) will be collected using questionnaires (Hibbard, Mahoney, Stockard, & Tusler, 2005; Bode, & de Ridder, 2008; Turner-Bowker, & Hoque, 2014). A questionnaire on experience of care has been considered, but no validated and appropriate questionnaires for this population are available. Therefore, for insight and rich information on the experienced care the format of a focus group was chosen.

Process evaluation:

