6. STATISTICAL ANALYSIS

Before analysis, all data will be cleaned improving data quality.

Quantitative data:

We will conduct intention-to-treat and per protocol analysis. We will use multilevel generalized linear models with the patient as the first level to correct for the repeated measures. The GP-practice (or cluster) will be the second level, and the group in which the GP practice is randomized will be the third level. We will adjust for level of integration, neighbourhood, time from start of study (continuous; with an interaction between cluster and time so that each cluster had its own underlying time trend), and total time on the randomised intervention, with time before intervention given as zero (continuous). Based on ICPC-codes used to select eligible patients, we will explore if subgroups can be identified in mainly (chronic) somatic, mainly mental or mainly social problems. Furthermore, analyses/ results will be stratification for sex. The analysis of the implementation will be descriptive.

Cost-effectiveness analysis/budget impact analysis:

The economic evaluation will consist of a trial-based cost-utility analysis (cost per QALY) with a time horizon of one year and a cost-utility analysis with a lifetime horizon (cost per QALY). Both analyses will be performed from a societal perspective. Next to this a Budget Impact Analysis will be performed according to the ISPOR Task Force principles.

Qualitative data:

Qualitative data will be collected through interviews or focus groups with care providers and patients and audiorecording. The interviews and focus groups will be conducted using a topic list based on experience of the pilot (protocol number **NL8223-10216**) and literature, to determine their satisfaction with the new approach.

The collected qualitative data will be analysed using both an inductive and deductive approach. This will be done by first transcribing the data and doing a thematic content analysis. After this, the data will be put into an initial coding book and further analysed until a final coding book is formed. The deductive analysis will be done using the positive health methodology. We will analyze whether positive health topics and techniques are being discussed and applied, as recommended by the methodology.

The audiotapes will be scored by two independent observers using the validated OPTION5 questionnaire.

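### As worded in section 4.2, a single P- or Z-chapter code on the problem list meets two of the three domains, so the rule admits some single-domain patients

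*Protocol*

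**What the plan says.** The participant criteria in section 4.2 state the general rule: "Patients have problems registered in the GP Information system on at least two out of three of the following domains". The three domains are then defined one at a time.

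- Somatic: "Somatic problems is having at least one ICPC code on the problem list". No chapter is named and none is excluded.
- Mental: "Mental problems is having at least one ICPC code from the 'P'-chapter on either the problem list, as a reason for encounter", or related medication.
- Social: "Social problems is having at least one ICPC code from the 'Z'-chapter or as reason for encounter", or related medication.

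Elsewhere the protocol describes the population in words. The Objectives say: "A hotspotter is a patient with problems on two out of three health domains (chronic somatic, psychiatric and/or social". The Summary, under Study population, has "problems on two out of three health domains (chronic somatic, mental and/or social problems) based on diagnosis". Section 4.1 asks for active problems in two of the three domains. The Summary and the Objectives qualify the somatic domain as chronic; section 4.2 does not.

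Section 4.1 also says how the criteria are used. The 60 patients ranked highest by the algorithm are screened against the inclusion criteria, and the GP's own list is checked against the inclusion and exclusion criteria. Both lists therefore rely on the definitions in 4.2.

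**The concern.** A two-of-three rule does its work only if the three conditions are distinct. Here they are not. P and Z codes are themselves ICPC codes, and section 4.2 itself names the problem list as a place where a P code may stand. Such a code fits the somatic definition as well as its own. For a patient with nothing else recorded, the two-domain rule becomes a one-domain rule.

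What is at stake is the match between the research question, which concerns patients with problems in multiple life domains, and the patients whom the criteria let in. Section 4.2 is the only place where the protocol turns the domains into something that can be checked in a record, so anyone who screens from the text as it stands can include patients outside the trial's own description of a hotspotter.

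**Working it through.** The plan gives no figure on this point, so there is nothing to reproduce. The check is logical.

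**Inputs, all from section 4.2.** Five yes/no items describe a patient's record:

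- S: a code outside chapters P and Z on the problem list
- Pp: a P code on the problem list
- Pr: a P code as reason for encounter, or mental-health medication
- Zp: a Z code on the problem list
- Zr: a Z code as reason for encounter, or medication for social problems

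This gives 2^5 = 32 patterns. The wording of the social clause is incomplete; it is read here as covering a Z code on the problem list, in parallel with the mental clause.

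**Domains.** Under both readings, mental = Pp or Pr, and social = Zp or Zr. The somatic domain differs:

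- literal reading: somatic = S or Pp or Zp
- distinct-domain reading: somatic = S

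A patient is eligible when at least two domains are positive.

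**Distinct-domain reading.** Mental is positive in 3 of the 4 combinations of Pp and Pr, and social likewise in 3 of 4.

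- S present and at least one other domain: 16 − 1 = 15 patterns
- S absent and both other domains present: 3 × 3 = 9 patterns
- Eligible: 15 + 9 = 24
- Single-domain: 1 (somatic only) + 3 (mental only) + 3 (social only) = 7
- No domain: 1
- Total: 24 + 7 + 1 = 32

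**Literal reading.** The 24 patterns stay eligible. The 7 single-domain patterns then behave as follows.

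| Record shows only | Somatic | Mental | Social | Eligible as written |
|---|---|---|---|---|
| S | yes | no | no | no |
| Pp | yes | yes | no | **yes** |
| Pp and Pr | yes | yes | no | **yes** |
| Pr | no | yes | no | no |
| Zp | yes | no | yes | **yes** |
| Zp and Zr | yes | no | yes | **yes** |
| Zr | no | no | yes | no |

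So 24 + 4 = 28 patterns are eligible as written, and 4 of the 32 are eligible with one real domain. Excluding P and Z codes from the somatic definition brings the 4 to 0. A P or Z code found only as reason for encounter, or a domain met only through medication, causes no double count.

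**Do other steps close the gap?** The exclusion criteria in 4.3 contain no domain check. The GP veto is discretionary. The algorithm in 4.1 is aimed at patients with problems in several life domains, but it ranks patients rather than enforcing two domains, and it does not govern patients found only through the GP's list. The requirement of two acute care encounters says nothing about domains.

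**The case against.** The strongest reply is that the clause defines somatic problems within a list that sets somatic apart from mental and social. In that context a psychological code is plainly not somatic, and no sensible screener would count it twice. The surrounding text supports this as the intended meaning. The reply is fair about intent, but it accepts that the written rule is wider than the rule meant, and eligibility text should not depend on the screener's charity.

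A second reply is that codes alone do not decide entry. The GP list starts from the GP's own judgement, the algorithm targets multi-domain patients, the GP can veto, and nothing says that the screening is automated. This stands as a reason to expect the number affected to be limited. It does not restore the two-domain requirement.

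A third reply is that the affected group is narrow: no problem-list code outside P and Z, a P or Z code on that list, and no sign of the other psychosocial domain. That is correct and limits the point.

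A reader might be tempted further, in four ways that the document does not support.

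- *The criterion as a whole misses its population.* Only the patterns marked above are affected, and their frequency is unknown.
- *The planned 25% cost reduction is diluted and the sample size of 200 is too small.* That needs the share of such patients and their response to the intervention. The protocol gives neither, and they would still be high users of acute care receiving the full intervention.
- *The somatic, mental and social subgroups in section 6 must overlap.* That section says only "Based on ICPC-codes used to select eligible patients, we will explore if subgroups can be identified", and it sorts patients by their main type of problem. Such a sorting need not reuse the eligibility flags.
- *Any trivial somatic complaint qualifies.* Somatic codes count only from the problem list, which may be meant as the filter for lasting problems, although the protocol does not say so.

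**Conclusion.** The point holds as a defect of wording with a real consequence: section 4.2 admits some patients with a problem in one domain only, against the two-of-three population in the Summary, the Objectives and section 4.1. It rests on the literal text of the somatic clause and on the absence of any other step that requires two distinct domains. It does not rest on a numerical assumption.

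Its size is 4 of 32 logical patterns, which says nothing about how common those records are. The number of enrolled patients affected cannot be derived from the document, and no effect on power, on the effect estimate or on the exploratory subgroups is claimed. The correction is worth making because the discrepancy is certain and the remedy is cheap. Separately, the qualifier chronic appears in the Summary and the Objectives but not in 4.2, and the two should agree.

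**What to change.** In section 4.2, state that a somatic problem is at least one ICPC code on the problem list from a chapter other than P and Z, and that one code counts for one domain only. The chapter exclusion is the essential part: a one-code rule alone would still let two P codes fill two domains. Apply the same mapping to the algorithm list and the GP list.

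Reconcile chronic across the Summary, the Objectives and 4.2. Either say that presence on the problem list is taken to mark a lasting problem, or define which codes count as chronic. The second option needs a code list that the protocol does not contain, so it is more work than the first.

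The main change costs one sentence and a consistent check at screening. Its downside is a slightly smaller eligible pool in each practice.
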